3.0 Main Protocol

BACKGROUND

General Overview:

Hyperglycemia during surgery has been linked to increased risk of postoperative complications, including wound infections, delayed wound healing, and cardiovascular events. Maintaining blood glucose within a target range during surgery has been shown to reduce the incidence of these complications. Two methods commonly used for maintaining blood glucose control intraoperatively are insulin drip and insulin boluses. However, the optimal method for achieving blood glucose control remains unclear. Therefore, we propose a randomized controlled trial to compare blood glucose control intraoperative between two groups using insulin drip in one group and insulin boluses in the other group.

Methodology

Inclusion criteria:

- All adult Diabetic patients (Both type I & Type II) undergoing Cardiac surgery with preoperative blood glucose level (80 -180 mg/dL)
- Patient with History of diabetes and those taking antidiabetic medications.

Exclusion criteria:

- Patients with known allergy or insulin intolerance.
- Patients with severe hepatic Dysfunction.

- Patient with History of hypoglycemic events in the past 6 month prior to surgery.

Randomization:

Simple randomization will be used for randomization. The participants will be randomized into two groups based on methods of insulin delivery.

- Group A: Insulin drip will be administered at a starting rate of 2 units/hour and titrated to maintain blood glucose levels between 80-180 mg/dL.
- Group B: Insulin boluses will be administered every 30 minutes to maintain blood glucose levels between 80-180 mg/dL.

Insulin boluses will be considered as a control group.

Statistical analysis:

The results will be presented as mean (SD), median (interquartile (range), or proportion. Using relative risk for statistical analysis and log rank. A P value of less than 0.05 will be considered statistically significant. Statistical analyses will be carried out using the SPSS or SAS.

4. SUBJECT SELECTION

4.1. Study Population:

All adult patients (above 18 y of age undergoing **Elective** Cardiac surgery with preoperative blood glucose level (80 -180 mg/dL)

4.2. Inclusion Criteria:

- All adult patients (above 18 y of age undergoing **Elective** Cardiac surgery with preoperative blood glucose level (80 -180 mg/dL)
- Patient with History of **Both Type I & Type II diabetes** and those taking antidiabetic medications.

4.3. Exclusion Criteria:

Patients with known allergy or insulin intolerance.

Patients with severe hepatic Dysfunction.

Patient with History of hypoglycemic events in the past 6 month prior to surgery.

4.4. Treatment

- Group A: Insulin drip will be administered at a starting rate of 2 units/hour and titrated to maintain blood glucose levels between 80-180 mg/dL.
- Group B: Insulin boluses will be administered every 30 minutes to maintain blood glucose levels between 80-180 mg/dL.

4.4.1 Material:

Insulin infusion

4.4.2 Preparation:

The medication will be prepared by the pharmacy

4.5. Supply of Study Drug at the Site

Insulin delivery are already in use and FDA approved there is no safety concerns at the time being

4.6. Storage: The hospital pharmacy

5. STUDY PROCEDURE

5.1. Study schedule

All adult patients (above 18 y of age undergoing Cardiac surgery with preoperative blood glucose level (80 -180 mg/dL) Patient with History of diabetes and those taking antidiabetic medications.

On admission, all patient will stop all preoperative anti diabetic medications and will be converted to Insulin short acting sliding scale as per protocol according to insulin requirement preoperatively. Patient requiring < 40 unites/ day will receive Low dose Insulin sliding scale, Patient requiring 40-80 unites/ day will receive Medium dose Insulin sliding scale and Patient requiring >80 unites/ day will receive High dose Insulin sliding scale. (Appendix 1)

5.1.1 Schedule of events

All demographic data, diagnosis, procedure (insulin delivery), surgery and hospital course details

Age, Sex, DM, HTN, NYHA class, HbA1C, Pre op FBS, Intraop lactate, Postop lactate, wound scale, BMI, BSA, Preop insulin, CKD, Pre antibiotic, Intraop antibiotic and length of stay will be collected from the day of admission to the day of discharge.

Data will be collected 24 hours before the surgery, then patients will be followed up immediately, one week after, one month, 6 months and one year.

Blood sugar level will be monitored hourly in the first postoperative day and every 4-6 hours during hospital stay.

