2.0 Protocol Synopsis

TITLE:

A Randomized Controlled Trial Comparing Blood Glucose Control Intraoperative Between Insulin Drip vs. Insulin Boluses

SPONSOR

No sponsor for this study

FUNDING ORGANIZATION

King Faisal Specialist Hospital & Research Center-Jeddah

NUMBER OF SITES

Only (King Faisal Specialist Hospital & Research Center-Jeddah)

RATIONALE:

This randomized controlled trial will provide valuable information on the optimal method for achieving blood glucose control intraoperatively. The results of this study may help improve patient outcomes and reduce the incidence of postoperative complications.

STUDY DESIGN:

Randomized Controlled Trial

PRIMARY OBJECTIVE:

Is to compare blood glucose control intraoperatively between patients who receive insulin drip and patients who receive insulin boluses during adult cardiac surgery.

SECONDARY OBJECTIVES:

Is to evaluate the incidence of hypoglycemic events and the need for insulin adjustments during surgery.

PRIMARY OUTCOME:

rate of severe hypoglycemia

SECONDARY OUTCOME:

-duration of ICU stay
-lactate clearance

-wound infection day 7; and day 30 (clinic follow-up)

NUMBER OF SUBJECTS:

If you assume that 6% of the participants receiving boluses will acquire a wound infection and 1% of the participants receiving insulin drip will acquire an infection, you will need to enroll the following number of participants in your study to detect this difference:

Assuming a two-sided test and an alpha = 0.05, to have power = 80% to detect the difference, you need to enroll 192 participants per group for a total of 384 participants.

SUBJECT SELECTION CRITERIA:

Inclusion Criteria:

- All adult patients (above 18 y of age undergoing Cardiac surgery with preoperative blood glucose level (80 -180 mg/dL)
- Patient with History of diabetes and those taking antidiabetic medications.

Exclusion Criteria:

- Patients with known allergy or insulin intolerance.
- Patients with severe hepatic Dysfunction.
- Patient with History of hypoglycemic events in the past 6 month prior to surgery.

TEST PRODUCT, DOSE, AND ROUTE OF ADMINISTRATION:

Insulin drip will be administered at a starting rate of 2 units/hour and titrated to maintain blood glucose levels between 80-180 mg/dL.

CONTROL PRODUCT, DOSE AND ROUTE OF ADMINISTRATION:

Insulin boluses will be administered every 30 minutes to maintain blood glucose levels between 80-180 mg/dL.

DURATION OF SUBJECT PARTICIPATION AND DURATION OF STUDY:

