8. DATA COLLECTION, HANDLING AND RECORD KEEPING

8.1 Case Report Form

All demographic data, diagnosis, procedure (insulin delivery), surgery and hospital course details Age, Sex, DM, HTN, NYHA class, **HbA1C**, Pre op FBS, Intraoperative lactate, Postop lactate, wound scale, BMI, BSA, Preoperative insulin, CKD, Pre antibiotic, Intraoperative Intraop antibiotic and length of stay will be collected from the day of admission to the day of discharge.

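### No intraoperative glucose measurement is specified for objectives that concern the operation, and nothing in the protocol makes glucose sampling equal between the arms

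*Protocol*

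**What the plan says.** The Synopsis (2.0) gives the primary objective: "Is to compare blood glucose control intraoperatively between patients who receive insulin drip and patients who receive insulin boluses during adult cardiac surgery". The secondary objective reads: "Is to evaluate the incidence of hypoglycemic events and the need for insulin adjustments during surgery". The primary outcome is "rate of severe hypoglycemia", with no glucose cut-off and no time window.

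The only monitoring frequency for glucose is in 5.1.1: "Blood sugar level will be monitored hourly in the first postoperative day and every 4-6 hours during hospital stay". Section 6 names blood sugar as the safety assessment without saying when it is taken.

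The data items in 5.1.1 include "HbA1C, Pre op FBS, Intraop lactate, Postop lactate, wound scale", and the CRF list in 8.1 includes "Pre op FBS, Intraoperative lactate, Postop lactate, wound scale, BMI, BSA". Both lists contain a preoperative fasting glucose and an intraoperative lactate. Neither names an intraoperative glucose.

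Section 4.4 describes the two arms. Group A, the drip arm, is described as follows: "Insulin drip will be administered at a starting rate of 2 units/hour and titrated to maintain blood glucose levels between 80-180 mg/dL". No interval for checking or adjusting is attached to it. For the control arm, Group B, the rule does carry a cadence: "Insulin boluses will be administered every 30 minutes to maintain blood glucose levels between 80-180 mg/dL".

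**The concern.** The trial compares two ways of holding glucose in range during an operation, yet its measurement schedule starts after the operation. A site that followed the protocol to the letter would have no scheduled glucose series for the period that both objectives name.

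The second difficulty is comparability. With no common schedule, each arm's insulin routine decides how often glucose is read in theatre. One arm has a fixed cadence and the other has none. An anaesthetised patient cannot report symptoms of a low glucose, so an episode is found only if a sample falls within it. The number of events counted then depends on the number of samples as well as on the true rate. Two arms with the same true rate could show different rates of severe hypoglycemia, and two arms with different true rates could look alike.

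An analysis plan cannot repair this. Readings never taken cannot be recovered, and sampling that depends on allocation cannot be reliably corrected afterwards.

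**Working it through.** **Step 1: the text side by side.**

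| Period | Stated glucose measurement | Where |
|---|---|---|
| Before surgery | Fasting glucose listed; eligibility needs a value of 80-180 mg/dL | 4.2, 5.1.1, 8.1 |
| During surgery, drip | None stated; titrated, no interval | 4.4 |
| During surgery, bolus | None stated; insulin every 30 minutes | 4.4 |
| First postoperative day | Hourly | 5.1.1 |
| Rest of hospital stay | Every 4-6 hours | 5.1.1 |

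The two rows for surgery are the ones the objectives concern, and neither has a measurement interval. The protocol gives no figure on this point, so there is nothing of its own to reproduce.

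**Step 2: how much unequal sampling could matter (illustration).** The inputs below are assumptions, not protocol values, except where noted.
- Equal true risk in both arms, and one episode per affected patient.
- Random onset; an episode is found only if a sample falls within it.
- Bolus arm sampled every 30 minutes, that is, one reading per dose. The protocol states the dosing interval only.
- Drip arm sampled every 15, 30, 60 or 120 minutes.

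For episode duration D and sampling interval I, the probability of detection is min(1, D/I). At equal true rates the apparent relative risk (drip v bolus) is min(1, D/I_drip) / min(1, D/30).

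| Episode | Bolus detection | Drip every 15 min | Drip every 30 min | Drip every 60 min | Drip every 120 min |
|---|---|---|---|---|---|
| 20 min | 20/30 = 0.67 | 1.00/0.67 = 1.50 | 0.67/0.67 = 1.00 | 0.33/0.67 = 0.50 | 0.17/0.67 = 0.25 |
| 30 min | 1.00 | 1.00 | 1.00 | 30/60 = 0.50 | 30/120 = 0.25 |
| 45 min | 1.00 | 1.00 | 1.00 | 45/60 = 0.75 | 45/120 = 0.38 |

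The bias is zero with equal sampling. It favors the drip if the drip arm is sampled less often and episodes are shorter than the drip interval. It favors the boluses if the drip arm is sampled more often than every 30 minutes and episodes last less than 30 minutes.

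**Step 3: chance of a false finding.** Take an assumed true risk of 5% in both arms, 30-minute episodes and the protocol's 192 patients per arm. The chance of a significant result favoring the drip (two-sided 0.05, exact binomial enumeration) should be at most about 2.5%.
- Drip every 60 minutes: expected observed rates 5% v 5% × 0.50 = 2.5%. The chance is about 25% with the chi-square test and 17% with Fisher's test.
- Drip every 120 minutes: 5% v 5% × 0.25 = 1.25%. The chance is about 58% with chi-square and 45% with Fisher.

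**The case against.** Several points on the other side stand.

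- A reader might infer that glucose is scheduled only after surgery. That is too strong: a preoperative fasting value is listed and eligibility requires a preoperative glucose. What is true is that the only stated monitoring frequency is postoperative.
- A reader might infer that hypoglycemia will be detected unequally, to the disadvantage of the bolus arm. The documents do not support this. The 30 minutes is a dosing interval, and a reading at each dose is a natural inference but not a stated rule. Holding the drip arm to the same range also needs readings, at an interval that could be equal, longer or shorter.
- An apparent twofold difference is one scenario. It needs a 60-minute drip interval, which appears nowhere in the protocol.
- The primary outcome has no stated window. Its link to surgery comes from the objectives, and the postoperative readings, scheduled alike for both arms, may contribute to the count.
- The CRF lists are not exhaustive. They open with general wording on insulin delivery, surgery and hospital course, and they do not name the postoperative glucose that 5.1.1 schedules. A hypoglycemic event could also be entered on the adverse event page (6.1.2). Absence from the lists therefore does not prove that a value goes unrecorded.

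None of this supplies an intraoperative sampling time, or makes sampling the same in both arms.

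**Conclusion.** The concern holds as a gap in measurement. The primary objective and the secondary objective on hypoglycemia during surgery have no specified intraoperative glucose measurement, and equal ascertainment between arms is not assured. This conclusion rests on the protocol text alone.

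The size and direction of any bias cannot be determined from the documents. Under the stated assumptions with 30-minute episodes, the apparent relative risk runs from 1.00 (no bias) to 0.25 as the drip interval goes from 30 to 120 minutes. With 20-minute episodes and a 15-minute drip interval it is 1.50, in the opposite direction. These figures show what the protocol leaves open and do not predict what will happen.

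The gap should be closed before enrolment, because it cannot be repaired in the analysis.

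**What to change.** 1. In 5.1.1, state one intraoperative glucose sampling schedule, identical in both arms, from the start of allocated insulin to leaving theatre. The investigators choose the interval.
2. In 5.1.1 and 8.1, add each intraoperative glucose value with its time to the CRF.
3. Fix the numeric cut-off and the time window of the primary outcome before the first patient.
4. Compare the arms on the common scheduled readings. Also report all severe hypoglycemia, including events found on unscheduled samples, so that no real event is lost.

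The cost is protocol and CRF wording, plus some additional glucose readings in whichever arm would otherwise be sampled less often. The change concerns measurement; the insulin rules themselves are left to the investigators.

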6. SAFETY ASSESSMENTS

Blood sugar level

6.1. Adverse Effects/Events (AEs)

Table 3. AE Relationship to Study Drug

6.1.1 Adverse event reporting period

The period for recording AEs in the CRF begins when signs the ICF and ends at the end of study visit.

6.1.2 Adverse Event Reporting

Both serious and non-serious AEs are to be reported on the AE page of the CRF as specified in the CRF data entry guidelines.

Relationship to Drug	Comment
Definitely	Previously known toxicity of agent; or an event that follows a reasonable temporal sequence from administration of the drug; that follows a known or expected response pattern to the suspected drug; that is confirmed by stopping or reducing the dosage of the drug; and that is not explained by any other reasonable hypothesis.
Probably	An event that follows a reasonable temporal sequence from administration of the drug; that follows a known or expected response pattern to the suspected drug; that is confirmed by stopping or reducing the dosage of the drug; and that is unlikely to be explained by the known characteristics of the subject's clinical state or by other interventions.
Possibly	An event that follows a reasonable temporal sequence from administration of the drug; that follows a known or expected response pattern to that suspected drug; but that could readily have been produced by a number of other factors.
Unrelated	An event that can be determined with certainty to have no relationship to the study drug.

The only foreseen adverse may be of the mouthwash giving a bitter taste.

6.2. Serious Adverse Experiences (SAE)

An SAE is defined as any AE occurring at any dose that results in any of the following outcomes:

1. Death
2. A Life-Threatening Adverse Experience
3. Inpatient Hospitalization or Prolongation of Existing Hospitalization
4. A Persistent or Significant Disability/Incapacity
5. A Congenital Anomaly/Birth Defect

Other important medical events may also be considered an SAE when, based on appropriate medical judgment, they jeopardize the subject or require intervention to prevent one of the outcomes listed.

6.2.1 Serious Adverse Experience Reporting:

1. Designee investigator(s) will document all SAEs that occur (whether or not related to study drug) per UCSF CHR Guidelines. The collection period for all SAEs will begin after informed consent is obtained and end after procedures for the final study visit have been completed.
2. In accordance with the standard operating procedures and policies of the KFSHRC's Institutional Review Board (IRB)/Independent Ethics Committee (IEC), the investigators will report SAEs to the IRB/IEC.

7. STATISTICAL ANALYSIS:

7.1 Sample size

This study will include a total of 384 adult patients randomly assigned to each arm (192 per arm).

7.2 Definition of study population

All adult patients (above 18 y of age undergoing Cardiac surgery with preoperative blood glucose level (80 -180 mg/dL) Patient with History of diabetes and those taking antidiabetic medications.

7.3 Overall statistical and analytical plan

This study will include a total of 384 adult patients randomly assigned to each arm (192 per arm). Sample size calculated basis of a two-sided test and an alpha = 0.05, to have power = 80%. The results will be presented as mean (SD), median (interquartile (range), or proportion. Using relative risk for statistical analysis and log rank. A P value of less than 0.05 will be considered statistically significant. Statistical analyses will be carried out using the SPSS or SAS.

8. DATA COLLECTION, HANDLING AND RECORD KEEPING

8.1 Case Report Form

All demographic data, diagnosis, procedure (insulin delivery), surgery and hospital course details Age, Sex, DM, HTN, NYHA class, **HbA1C**, Pre op FBS, Intraoperative lactate, Postop lactate, wound scale, BMI, BSA, Preoperative insulin, CKD, Pre antibiotic, Intraoperative Intraop antibiotic and length of stay will be collected from the day of admission to the day of discharge.

8.2 Source Data

Source documentation is defined as the first time data appear, and may include original documents, data and records (e.g., hospital records, clinical and office charts, procedure reports, laboratory notes, memoranda, pharmacy dispensing records, recorded data from automated instruments, copies or transcriptions certified after verification as being accurate copies, subject files, and records kept at the pharmacy, at the laboratories). Information in source documents (i.e., medical history/physical condition) dated prior to the Patient Information and Informed Consent Form signature date may be used to verify patient eligibility criteria.

Clinical records must be marked to indicate a subject has been enrolled into the clinical study. The Investigator must ensure the availability of source documents from which the information on the CRFs was derived. Where printouts of electronic medical records are provided as source documents, or where copies of source documents are retained as source documents, they should be signed and dated by a member of the investigational site team indicating they are a true reproduction of the original source document.

Clinical Investigation Plan

The source documents must be made available for monitoring or auditing. Copies of source documents will be requested to support event adjudication.

Data will be collected through ICIS power chart and will be entered into a secured database. A data management plan will be created before data collection begins and will describe all functions, processes, and specifications for data collection, cleaning and validation. Concurrent manual data review will be performed based on parameters dictated by the plan. High quality standards will be maintained, and processes and procedures utilized to repeatedly ensure that the data are clean and accurate as possible when presented for analysis.

8.3 Protocol Deviations

A study deviation is an event where the investigator or site personnel did not conduct the clinical study according to the Clinical Investigational Plan. The investigator is not allowed to deviate from the above-mentioned documents except with prior approval and under emergency circumstances. All deviations shall be documented and explained, regardless the reason for the deviation.

In this study where all patients receive standard hospital care, reporting of deviations is only required in case informed consent cannot be obtained before data entry. No further data should be entered until the issue has been resolved. Failure to obtain consent from the patient to release personal information might ultimately result in removing the patient from the study.

The investigator is obliged to comply with Ethical Committee procedures and/or local laws for reporting deviations.

9. ADMINISTRATIVE, ETHICAL, REGULATORY CONSIDERATIONS

9.1. Investigator Responsibilities

Informed consent is defined as a legally effective documented confirmation of a subject's or their legally authorized/designated representative's voluntary agreement to participate in a particular study after information has been given and explained to the subject on all aspects of the study that are relevant to the subject's decision to participate.

Here and throughout the document, "EC/IRB" is the term that will be used collectively in reference to an Institutional Review Board (IRB), Ethics Committee (EC).

It is the responsibility of the investigator to confirm the approval requirements of the hospital and local regulations for this observational study with his/her EC/IRB prior to start of the study. As a minimum, it is strongly recommended notifying the local Ethics Committee about the conduct of this study.

Patients' confidentiality will be maintained, removing any identifying informations from the data set by the data controller before further usage and analysis. The data of both variables and their values were coded into Alpha-numeric format for concealment with few designated persons having the coding key.

The study will be conducted according to the Declaration of Helsinki and Council for International Organizations of Medical Sciences (CIOMS) International Ethical Guidelines. It will also follow the International Council for Harmonization (ICH) Good Clinical Practice (GCP) Guidelines

Patient engagement and withdrawals:

A participant may withdraw from the study at any time, at his/her own request or may be withdrawn at any time at the discretion of the Investigator for safety, behavioral, compliance, or administrative reasons. A participant will be considered lost to follow-up if he or she repeatedly fails to return for scheduled visits and is unable to be contacted by the study site.

Regulatory and Ethical Considerations:

- This study will be conducted in accordance with the protocol and the following:
 - Consensus ethical principles derived from international guidelines, including the Declaration of Helsinki and Council for International Organizations of Medical Sciences (CIOMS) International Ethical Guidelines
 - Applicable ICH GCP Guidelines
 - Applicable laws and regulations
- The Investigator must submit the protocol, protocol amendments (if applicable), ICF, and other relevant documents to an IRB/IEC and the IRB/IEC must review and approve them before the study is initiated.
- Any protocol amendments (i.e., changes to the protocol) will be documented in writing and require IRB/IEC approval before implementation of changes, except for changes necessary to eliminate an immediate hazard to study participants. When applicable, amendments will be submitted to the appropriate Health Authorities.
- The Investigator will be responsible for the following:
 - o Providing written summaries of the status of the study to the IRB/IEC annually or more frequently per the IRB's/IEC's requirements, policies, and procedures.
 - o Notifying the IRB/IEC of SAEs or other significant safety findings, as required by IRB/IEC procedures
 - o Providing oversight of the study conduct at the site and adherence to requirements of ICH guidelines, the IRB/IEC, for clinical studies (if applicable), and all other applicable local regulations

Publication:

- The results of this study may be published or presented at scientific meetings. If this is Foreseen.

- The investigator will comply with the requirements for publication of study results. Per standard editorial and ethical practice.
- Authorship will be determined by agreement and in line with International Committee of Medical Journal Editors authorship requirements.

Data Quality Assurance:

- All participant study data will be recorded on printed or electronic CRFs or transmitted to the designee electronically (e.g., laboratory data). The Investigator is responsible for verifying that data entries are complete, accurate, legible, and timely by physically or electronically signing the CRF.
- The Investigator must maintain accurate documentation (source data) that supports the information in the CRF.
- The Investigator must permit study-related monitoring, quality assurance audits, IRB/IEC review, and regulatory agency inspections and provide direct access to the study file and source data.
- Monitoring details describing strategy (e.g., risk-based initiatives in operations and quality such as Risk Management and Mitigation Strategies and Analytical Risk-Based Monitoring), methods, responsibilities and requirements.
- Records and documents, including signed ICFs, pertaining to the conduct of this study must be retained by the Investigator for 15 years after study completion, unless local regulations, institutional policies. No records may be destroyed during the retention period without the Sponsor's written approval.

Protocol adherence and amendments:

Adherence to the study design requirements, including those specified in the SoA, is essential and required for study conduct.

Informed Consent Form:

If full Informed Consent is requested by local laws or by the EC/IRB, a signed “Patient Informed Consent” (PIC) document should be obtained. In this case, a patient informed consent form will be given to each patient, which includes all aspects of the clinical study that are relevant to the subject’s decision to participate throughout the clinical study.

The informed consent form will be translated into the appropriate language of each country in which the study will be conducted.

Each patient and Principal Investigator or authorized delegated designee obtaining informed consent must personally sign and date, in the appropriate local language a “Patient Informed Consent Form”.

The physician must keep the original informed consent form signed by the patient (a signed copy is given to the patient). For subjects that are unable to read or write, the informed consent shall be obtained through a supervised oral process. The independent witness shall be present throughout the entire process. The informed consent form and any other information shall be read aloud and explained to the subject, and whenever possible, either shall sign and personally date the informed consent form. The witness also signs and personally dates the informed consent form attesting that the information was accurately explained and that informed consent was freely given.

Where a patient has initially verbally consented or a patient’s legally acceptable representative has consented on behalf of the patient, written consent should be sought from the patient as soon as, in the investigator’s opinion, the patient is capable of understanding the process and capable of signing the consent form.

10. REFERENCES:

